#### **12.4 Archiving Study Records**

Per 21 CFR 312.62(c), Investigators shall retain records required to be maintained under this part for a period of 2 years following the date a marketing application is approved for the drug for the indication for which it is being investigated, or, if no application is to be filed or if the application is not approved for such indication, until 2 years after the investigation is discontinued and FDA is notified. However, documents may be retained for a longer period if required by the applicable legal requirements.

The Sponsor will maintain archive copies of all records for a period of no less than 25 years.

### **13. PUBLICATION POLICY**

By signing the study protocol, the Investigator agrees with the use of results of the study for the purposes of national and international registration, publication, and information for medical and pharmaceutical professionals. If necessary, Regulatory Authorities will be notified of the Investigator's name, address, qualifications, and extent of involvement.

An Investigator shall not publish any data (poster, abstract, paper, etc.) without discussion with and approval by the Sponsor.

## LIST OF ABBREVIATIONS

Abbreviation	Term
AE	Adverse event
ALT	Alanine aminotransferase
AST	Aspartate aminotransferase
BICR	Blinded independent central review
BMI	Body mass index
CCDD	Centrally confirmed dedifferentiated
CDK4	Cyclin dependent kinase 4
CDKN2A	cyclin-dependent kinase inhibitor 2A
CI	Confidence interval
CMH	Cochran-Mantel-Haenzel
CR	Complete response
CSR	Clinical Study Report
CTCAE	Common Terminology Criteria for Adverse Events
ctDNA	Circulating rumor DNA
DCR	Disease control rate
DOR	Duration of response
ECOG	Eastern Cooperative Oncology Group
ECG	Electrocardiogram
eCRF	Electronic case report form
EORTC QLQ-C30	European Organization for the Research and Treatment of Cancer Quality of Life Questionnaire
FDA	United States Food and Drug Administration
IDMC	Independent data monitoring committee
ITT	Intent to treat
IRT	Interactive response technology
MDM2	Mouse double minute 2
ORR	Objective response rate
OS	Overall survival
PD	Progressive disease
PFS	Progression-free survival
PK	Pharmacokinetics
PR	Partial response
PRO	Patient reported outcomes

PT	Preferred term
QoL	Quality of life
RECIST	Response Evaluation Criteria in Solid Tumors
RMST	Restricted mean survival time
SAE	Serious adverse event
SAP	Statistical analysis plan
SD	Stable disease
SOC	System organ class
TEAE	Treatment-emergent adverse event
TP53	Tumor protein 53
ULN	Upper limit of normal

## **1. INTRODUCTION**

This statistical analysis plan (SAP) outlines the statistical methods to be implemented for study RAIN-3201 entitled “A Randomized Multicenter Phase 3 Study of Milademetan Versus Trabectedin in Patients with Dedifferentiated Liposarcoma”. The purpose of the SAP is to ensure the credibility of the study findings by pre-specifying the statistical approaches to the analysis of study data prior to the primary analysis. Results of the planned analyses in this SAP will become the basis of the clinical study report (CSR) for this protocol.

## **2. STUDY OBJECTIVES**

### **2.1. Primary Objective**

The primary objective is to assess the effect of milademetan versus trabectedin on progression-free survival (PFS) per Response Evaluation Criteria in Solid Tumors (RECIST) version 1.1 as determined by blinded independent central review (BICR) in patients with unresectable or metastatic dedifferentiated (DD) liposarcoma, with or without a well-differentiated (WD) component, who progressed on 1 or more prior systemic therapies including at least 1 anthracycline-based therapy.

### **2.2. Secondary Objectives**

The secondary objectives are:

- To compare the milademetan treatment arm versus the trabectedin control arm for the following efficacy measures:
  - Overall survival (OS)
  - Disease control rate (DCR) by BICR and by Investigator
  - Objective response rate (ORR) by BICR and by Investigator
  - Duration of response (DOR) by BICR and by Investigator
  - PFS by Investigator assessment
- To assess the safety profile of milademetan
- To evaluate patient-reported outcomes of milademetan

### **2.3. Exploratory Objectives**

### **3. STUDY DESIGN OVERVIEW**

#### **3.1. Overall Design**

This is a randomized, multicenter, open-label, Phase 3 registration study designed to evaluate the safety and efficacy of milademetan compared to trabectedin in patients with unresectable (i.e., where resection is deemed to cause unacceptable morbidity or mortality) or metastatic DD liposarcoma that progressed on 1 or more prior systemic therapies, including at least 1 anthracycline-based therapy.

Approximately 160 patients will be randomly assigned in a 1:1 ratio to receive milademetan or trabectedin. Randomization will be stratified by Eastern Cooperative Oncology Group (ECOG) performance status (0 or 1) and number of prior treatments ( $\leq 2$  or  $> 2$ ) for the patient's liposarcoma.

Patients will receive study drug (i.e., milademetan or trabectedin) until reaching disease progression per RECIST 1.1 as determined by the Investigator, experiencing unmanageable toxicity, or until other treatment discontinuation criteria are met. Patients may be treated beyond tumor progression if they are experiencing clinical benefit based on the assessment of the Investigator in discussion with the Medical Monitor. All patients will be followed for documentation of disease progression and survival information (i.e., date and cause of death) and subsequent treatment information (i.e., date/duration of treatment, response, and subsequent disease progression). Long-term follow-up will continue every 12 weeks ( $\pm 7$  days) until the endpoint of death, the patient is lost to follow-up, or for 24 months following the final dose of study drug, whichever comes first.

#### **3.2. Sample Size Considerations**

## **4. STUDY ENDPOINTS AND COVARIATES**

### **4.1. Primary Endpoint**

The primary efficacy endpoint is PFS defined as the time from the date of randomization to the date of documented disease progression as determined per RECIST 1.1 by BICR or death due to any cause, whichever comes first.

### **4.2. Secondary Endpoints**

Secondary efficacy endpoints include:

- OS defined as the time measured from the date of randomization to the date of death by any cause
- DCR defined as the percentage of patients who have achieved complete response (CR), partial response (PR), or stable disease (SD) for  $\geq 16$  weeks as determined by BICR/Investigator using RECIST 1.1.
- ORR defined as the percentage of patients who achieve a confirmed CR or PR as determined by BICR/Investigator using RECIST 1.1.
- DOR defined as the time from date of first objective response (CR or PR) to date of disease progression as determined by BICR/Investigator using RECIST 1.1. or death, whichever comes first
- PFS defined as the time from the date of randomization to the documented disease progression based on Investigator assessments as determined per RECIST 1.1 or death due to any cause

Health-related quality of life (HRQoL) endpoints include:

- European Organisation for Research and Treatment of Cancer (EORTC) Quality-of-Life Questionnaire, Core 30 (QLQ-C30)

Safety endpoints include:

- Incidence of treatment-emergent adverse events (TEAEs) including serious adverse events (SAEs)
- Incidence of TEAEs leading to discontinuation of study drug
- Incidence of TEAEs leading to study withdrawal
- Incidence of deaths
- Changes in clinical laboratory parameters (hematology, serum chemistry, coagulation, urinalysis, and serum and urine pregnancy test), vital signs, and electrocardiogram (ECG) parameters (especially QT intervals); physical examination results (including ECOG performance status); and use of concomitant medications.

#### **4.3. Exploratory Endpoints**

[REDACTED]

#### **4.4. Baseline Covariates**

The following covariates will be used to examine efficacy in subgroups or in multivariate analyses:

- ECOG performance status: 0 vs. 1
- Number of prior anti-cancer treatments:  $\leq 2$  vs.  $>2$
- Prior therapy for advanced/metastatic disease: Yes vs. No
- Region: North America, Europe, and Rest of World
- Age:  $< 65$  vs.  $\geq 65$  years
- Sex: male vs. female
- Race: white and other categories depending on frequency observed
- Well differentiated liposarcoma component: yes vs. no

Covariate values may be discordant if collected via electronic case report form (eCRF) and interactive response technology (IRT) (ECOG performance status, number of prior treatments). For subgroup and multivariate model analyses, the source verified eCRF value will be used to reflect the true clinical relevance of the covariate. For stratified treatment comparisons, however, the IRT value will be used to be consistent with the randomization scheme.

### **5. ANALYSIS POPULATIONS**

#### **5.1. Intent-to-treat (ITT) Population**

The intent-to-treat (ITT) population is defined as all subjects who are randomized into the study. Patients will be analyzed according to treatment arm to which they were randomized regardless of treatment received.

[REDACTED]

## **5.2. Safety Population**

The Safety Population is defined as all randomized patients who received at least one dose of investigational product. Patients will be analyzed based on the treatment actually received regardless of the treatment to which they were randomized.

All safety analyses will be performed using the Safety Population.

## **5.3. Pharmacokinetics (PK) Population**

The pharmacokinetics population consists of all randomized patients who received at least one dose of milademetan for whom data on concentrations of study treatment is available.

[REDACTED]

## **5.4. Quality of Life (QoL) Population**

The QoL population consists of all patients in the ITT population for who have a baseline and at least one post baseline QoL assessment.

[REDACTED]

## **5.5. Centrally Confirmed Dedifferentiated Liposarcoma (CCDD) Population**

The Centrally Confirmed Dedifferentiated Liposarcoma Population is defined as all patients with centrally confirmed dedifferentiated liposarcoma disease.

[REDACTED]

[REDACTED]

## **5.7. Per Protocol Population**

The Per Protocol Population consists of all randomized patients who have no important protocol deviations thought to impact the efficacy analysis.

[REDACTED]

## **6. INTERIM ANALYSIS AND DATA MONITORING**

[figure not shown]
No interim PFS analysis is planned. One OS interim analysis is planned at the time of the primary PFS analysis. The final OS analysis will be performed at the end of the study when all patients complete the 24-month long-term follow-up.

An independent data monitoring committee (IDMC) will review accumulating data periodically throughout the study and to make recommendations to the Sponsor regarding the conduct of the study in order to safeguard the interests of trial participants while preserving the integrity and credibility of the study. The Sponsor will implement guidelines to provide internal access of unblinded data on a strictly as required basis for the purpose of data capture, cleaning and analysis of this study. An independent biostatistician external to the Sponsor will prepare analyses for the IDMC.

## **7. STATISTICAL METHODS OF ANALYSIS**

### **7.1. General Principles and Reporting Conventions**

The primary goal of the statistical analysis of the study is to demonstrate whether there is an increase in PFS in subjects treated with milademetan versus trabectedin in ITT population. The timing of the primary analyses of PFS will be event-driven based on corresponding pre-specified goals for the target number of 105 PFS events in the ITT population. The primary analysis of PFS and other RECIST endpoints will be according to BICR. Sensitivity analyses using investigator assessed tumor response or disease progression will be performed, using similar analysis sets of local review.

## **7.2. Subject Accountability**

### **7.2.1. Disposition of Patients**

The number and percentage of patients who were screened, randomized and treated with study drug, randomized but not treated with study drug will be tabulated by treatment arm. The number and percentage of patients in each analysis population will be tabulated by treatment arm.

Screen failures will be summarized with reasons. The number and percentage of patients entering and completing each phase of the study will be presented by treatment. End of treatment and end of study will be summarized by reasons.

### **7.2.2. Protocol Deviations**

Protocol deviations will be classified and monitored regularly during the duration of the study. Among other reasons, failure to meet any of the protocol inclusion or exclusion criteria will be considered a protocol deviation. All protocol deviations will be listed and summarized by type and treatment group. Important protocol deviations, thought to potentially impact the study conclusions, will be listed and tabulated using incidence and percentage by deviation type and treatment arm.

## **7.3. Demographic and Baseline Characteristics**

Descriptive statistics will be provided for all demographic and baseline disease characteristics based on the ITT population. Demographic data, medical history, concomitant disease, and concomitant medication will be summarized by means of descriptive statistics or frequency tables, overall and stratified by treatment.

### **7.3.1. Demographic Characteristics**

The following demographic variables will be summarized by treatment group:

- age (years)
- age group (<65,  $\geq$  65 years; <65, 65 – 85,  $\geq$  85 years)
- sex
- race & ethnicity
- region (North America, Europe, and Rest of World)

- height (cm)
- weight (kg)
- body mass index (BMI) calculated as:  $BMI \text{ (kg/m}^2\text{)} = \text{Weight (kg)} / (\text{Height(cm)} \times 0.01)^2$

### **7.3.2. Randomization Stratification Factors**

### **7.3.3. Baseline Disease Characteristics**

The following baseline disease characteristics will be summarized by treatment group:

- Stage at initial diagnosis
- Stage at study entry
- Tumor differentiation
- Mitotic count
- Tumor necrosis
- FNCLCC grade
- TNM stage at study entry
- Time from initial diagnosis to randomization
- Time from metastatic diagnosis to randomization
- Tumor status
- Metastatic sites

[figure not shown]
### **7.3.4. Prior Cancer Therapy**

Prior radiation, cancer related surgery, cancer therapy will be summarized with indication and by treatment arm. Number of prior lines of therapy for metastatic disease, best response and reason for treatment discontinuation of each therapy will be summarized by treatment arm.

### **7.3.5. Medical History**

Medical history data including chronic conditions, relevant surgical procedures, symptoms, any medical conditions that require medication and cancer history will be collected at screening, within 14 days before Cycle 1 Day 1. Medical history data will be summarized and listed by treatment arm.

#### **7.4. Efficacy Analyses**

#### **7.4.1. Progression Free Survival (PFS)**

Progression free survival (PFS) is defined as the time interval from the date of randomization until the first date on which progression (per RECIST v1.1) or death due to any cause, is documented, whichever comes first. Assessment of PFS will be performed for all patients at baseline, at the end of W8, W16, W24, W32, and then every 12 weeks ( $\pm$  1 week), regardless of treatment schedule modification (e.g., dose delay), until documented disease progression, initiation of new anticancer therapy, or discontinuation from the study (death, withdrawal of consent, or loss to follow-up). Subjects without documented progressive disease (PD) or death, including those who dropped out, will be censored at their last tumor assessment. Patients who did not have any tumor assessments after the screening visit will be censored on the randomization date.

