Primary Endpoint: PFS by BICR	Secondary Endpoints: OS, ORR, DOR, DCR, PFS by Investigator assessment, HRQoL, and safety evaluations
Assumptions: 

For the trabectedin arm (standard of care), median PFS <math>\leq</math> 3 months

Estimated median PFS = 6 months with milademetan

	

Final analysis for the primary endpoint will occur after 105 PFS events

Intensive ECG and PK Evaluation in a Subgroup of Milademetan-Treated Patients	
A subset of approximately 25 patients enrolled across several milademetan (RAIN-32) studies, including the current study, will undergo intensive ECG and PK evaluation at selected study centers.
 
Patients in the ECG/PK subgroup must meet the following criteria to participate in the additional ECG and PK evaluation (if these criteria are not met patients can still participate in the study but will not participate in intensive ECG and PK evaluation):
 

Has a corrected QT interval (QTc) as calculated according to Fridericia's formula (QTcF) <math>\leq</math> 450 ms

Does not have atrial fibrillation or atrial flutter

Does not have complete left bundle branch block

Does not have an implanted pacemaker or defibrillator

Does not have a history of Long QT Syndrome, Brugada Syndrome, Wolff Parkinson White Syndrome, or aborted sudden cardiac death

 
In this subset of patients, PK blood samples will be collected on Cycle 1 Day 1 (predose and at 1, 2, 3, 4, 6, 8, and 24 hours after dosing) and Cycle 1 Day 3 (predose and at 1, 2, 3, 4, 6, 8, and 24 hours after dosing). Patients will wear continuous 12-lead Holter recorders from 1 hour before their milademetan dose through 24 hours after their dose on Cycle 1 Day 1 and Cycle 1 Day 3. Each ECG will be extracted from a supine rest period of at least 10 minutes. The PK samples will be collected immediately after the supine rest period.

[figure not shown]
Investigational Treatment (Milademetan)	
[REDACTED]
 
Dose and Mode of Administration: 260 mg once daily (QD) on Days 1 to 3 and Days 15 to 17 of each 28-day cycle.

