## 4.2 Imaging Assessments by Blinded Independent Central Review

### 4.2.1 Intensive Electrocardiogram and Pharmacokinetics Evaluation in a Subgroup of Milademetan-Treated Patients

## **4.3 Endpoints and Criteria for Evaluation**

### **4.3.1 Primary Endpoint**

The primary efficacy endpoint is PFS defined as the time from randomization to the earliest date of the first objective documentation of radiographic disease progression as determined by BICR or death due to any cause. Tumor response will be assessed in accordance with RECIST version 1.1.

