### **11.3 Duration of the Study**

The total study duration is estimated to be 4 years, including approximately 12 months for accrual of patients, up to 12 months of treatment for each patient, and up to 24 months of long-term follow-up following the first dose of study drug of the last patient enrolled. The end of the study is defined as the last patient visit or contact, including telephone contacts, for collection of any study-related data.

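### SAP 7.4.1: the day-0 censoring sentence omits the limit to patients without documented PD or death and, taken literally, conflicts with the PFS definition (minor wording conflict)

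*SAP*

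**What the plan says.** SAP 7.4.1 does three things in turn.

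- It defines the event as progression "or death due to any cause, is documented, whichever comes first".
- It gives the general censoring rule: "Subjects without documented progressive disease (PD) or death, including those who dropped out, will be censored at their last tumor assessment".
- It closes with: "Patients who did not have any tumor assessments after the screening visit will be censored on the randomization date".

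SAP 4.1 defines the primary endpoint by progression "as determined per RECIST 1.1 by BICR or death due to any cause, whichever comes first". Protocol 4.3.1 agrees: "radiographic disease progression as determined by BICR or death due to any cause". None of these definitions requires a post-baseline scan before a death can count.

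The first scheduled post-baseline assessment is at the end of Week 8. SAP 7.1 triggers the primary analysis at a "target number of 105 PFS events in the ITT population".

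**The concern.** The second sentence applies only to patients with neither PD nor death. The third has a single trigger, the absence of any post-screening assessment, and makes no exception for deaths. A patient who dies before Week 8 without an unscheduled scan therefore meets the event definition and also the literal condition for censoring at randomization. No visible sentence says which prevails. Only deaths are affected, because a patient with no post-screening scan cannot have radiographic PD.

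The rule feeds the primary endpoint of a registration trial and the event count that sets the analysis date. Programmed literally, it would remove early unscanned deaths from the PFS comparison and postpone the trigger. The deaths would still appear in OS and, for treated patients, in the safety tables.

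**Working it through.** **Step 1: the text.** Take a patient who dies in Week 5 with no scan after screening.

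| Rule | Result |
|---|---|
| PFS definition (SAP 7.4.1, SAP 4.1, protocol 4.3.1) | Event on the date of death |
| General censoring sentence (SAP 7.4.1) | Does not apply, because the patient has died |
| Day-0 sentence, read literally | Censored at randomization |
| Day-0 sentence, read as a sub-case of the general rule | Does not apply; the event stands |

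The first and third rows conflict. The fourth removes the conflict, but the sentence does not say that it is a sub-case. SAP 7.4.5 (DOR) does limit its censoring to patients without PD or death.

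**Step 2: inputs for the size.**

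- About 160 patients, 1:1, so 80 per arm (SAP 3.1).
- Control median PFS of 3 months, the upper limit of the synopsis assumption; "Estimated median PFS = 6 months with milademetan". With exponential PFS the HR is 3/6 = 0.50.
- Uniform accrual over 12 months (protocol 11.3: "approximately 12 months for accrual of patients"); no dropout (assumed).
- Week 8 = 8/4.345 = 1.84 months.
- Unscanned early deaths in 2.5% to 10% of patients. This range is an assumption; the documents give no rate.

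The 105 events cannot be reproduced, because alpha and power are not in the visible text.

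**Step 3: delay, in closed form.** With hazard λ = ln 2/median, expected events per arm by month T (T at least 12) are

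80 × {1 − [exp(−λ(T−12)) − exp(−λT)]/(12λ)}.

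At T = 13.5:

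- trabectedin: 80 × [1 − (0.7071 − 0.0442)/2.7726] = 60.9
- milademetan: 80 × [1 − (0.8409 − 0.2102)/1.3863] = 43.6
- total: 104.5

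The expected count reaches 105 at month 13.56. If 4, 8 or 16 deaths are not counted (2.5%, 5% or 10% of 160), the trial must wait for 109, 113 or 121 events in all. These come at months 14.05, 14.58 and 15.83, which are delays of 0.49, 1.02 and 2.26 months.

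**Step 4: effect on the HR.** Simulation with 1,500 replicates per case and the Step 2 inputs. PFS already includes deaths, so the unscanned deaths were drawn from events before Week 8 and not added to the curves. Each analysis was cut at its own 105th counted event and gave a Cox HR.

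| Unscanned early deaths (assumed) | Mean HR, counted | Mean HR, literal rule | Shift | Delay (months) |
|---|---|---|---|---|
| 2.5% of patients, both arms | 0.510 | 0.499 | −0.011 | 0.49 |
| 5% of patients, both arms | 0.508 | 0.484 | −0.024 | 1.02 |
| 10% of patients, both arms | 0.509 | 0.464 | −0.045 | 2.28 |
| 5%, milademetan only | 0.506 | 0.459 | −0.047 | 0.49 |
| 5%, trabectedin only | 0.507 | 0.532 | +0.025 | 0.49 |
| 18.6% of early events, each arm (about 8 deaths) | 0.510 | 0.507 | −0.003 | about 1 |

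Repeat runs with other seeds gave 0.506 to 0.510 (counted) and 0.481 to 0.487 (literal) for 5% in both arms. Dating progression at the scheduled scans gave 0.514 and 0.487 for that case, with a delay of 1.07 months.

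**Step 5: why the pattern matters.** P(event before Week 8) = 1 − 0.5^(1.84/median), which is 34.6% on trabectedin and about 19% on milademetan. An equal 5% of patients is therefore 5/34.6 = 14% of early trabectedin events but 5/19 = 26% of early milademetan events. The literal rule then removes proportionately more milademetan events, and the HR falls. When the removed share of early events is equal, the HR hardly moves.

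**Step 6: scale.** The standard error of the log HR is about 2/√105 = 0.195. On the HR scale near 0.50 this is 0.50 × 0.195 = 0.098, close to the simulated SD of about 0.10.

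**The case against.** The strongest reply is that the conflict appears only when the last sentence is taken out of its paragraph. The paragraph defines the event, then says who is censored and when, then supplies a date for those who have no post-baseline assessment to be censored at. Read in that order, a patient who died has already had an event and never reaches the censoring rules. This is the natural reading, and it stands. What remains is that the sentence does not say so, and a primary-endpoint rule should not depend on the programmer's choice of reading.

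Second, text that could settle the point is not visible: the bodies of SAP 7.5.1 and 7.5.2, and all of protocol Section 9, whose contents list includes the primary PFS analysis (9.7.1). This also stands. Its absence from the public text is not a fault in the plan.

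A reader might go on to draw three stronger conclusions, which the documents do not support:

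- *That early deaths will be dropped from the primary analysis.* Only the less natural reading of one sentence implies this.
- *That the rule favours milademetan.* The direction depends on the pattern of deaths, on which the documents are silent. Even equal rates in both arms favour milademetan only if they are equal percentages of patients.
- *That power is lost.* The analysis waits for 105 counted events, so uncounted deaths are replaced by later events. The cost is time.

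**Conclusion.** A real but minor wording conflict. Followed as written, the day-0 sentence in SAP 7.4.1 gives an unscanned death a result that contradicts the PFS definition in the same paragraph, in SAP 4.1 and in protocol 4.3.1. It is not evidence of what the sponsor intends or will program.

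Under assumed unscanned-death rates of 2.5% to 10% of patients in both arms, literal application would lower the mean HR by about 0.01 to 0.05 and delay the 105th event by about 0.5 to 2.3 months. The HR moves in milademetan's favour if such deaths occur on milademetan only or in an equal percentage of patients per arm. It moves toward 1 if they occur on trabectedin only. It hardly moves if they are an equal share of early events, and then only the delay remains. All these shifts are well within the HR's sampling SD of about 0.10.

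The figures rest on exponential PFS with medians of 3 and 6 months, uniform 12-month accrual, no dropout, and death rates that are not in the documents. The textual conflict depends on none of these assumptions.

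**What to change.** Open the last censoring sentence of SAP 7.4.1 with **Patients without documented PD or death who**, and leave the rest as it stands. Unscanned deaths then remain events under the existing definition, and no new rule is needed. The change should be subject to, and agree with, any rule in SAP 7.5.1, SAP 7.5.2 or protocol Section 9. Apply the same wording to BICR and investigator PFS, and check both derivations before unblinding, including a test case who dies with no post-screening scan.

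The cost is one clause in the SAP and one programming check. Data collection, the sample size and the 105-event target do not change.
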